# 2.5. MATERIAL AND METHOD

## 2.5.1. SAMPLE

## 2.5.1.1. SAMPLE CHARACTERISTICS

During the initial calculation of the sample number, the number of the participants was determined, with purpose, the method of Analysis of Variance (ANOVA) in two groups of equal population, to identify a standardized effect size equal to 0.25 with a power of 80% and a level of statistical significance of 5%. The standardized effect size is defined as follows: Let the measurement tool X and groups A, B and  $\mu$ A,  $\mu$ B

be the mean values of X in groups A and B. SD is the Standard Deviation of X in the whole population. The effect size is given by the formula  $(|\mu A-\mu B|)/SD$ . The calculation was performed with the program G\*power version 3.1.9.7\* and the necessary sample size was calculated at 126 subjects. According to the relevant literature, similar standardized sample sizes have been used in two studies dealing with chronic neck pain (Lundblad *et al.*, 1999; Malmgren-Olsson *et al.*, 2009). Moreover, a dropout rate of 20% was expected, so a final number of around 152 patients is realistic for this study.

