## 2.5.1.2. METHOD OF RANDOMIZATION AND BLINDING

The sample will include 152 patients of both sexes and age range 19-70 years. Participants will be collected using the simple random sampling method and these meeting the inclusion and exclusion criteria will be recruited and will form the study sample. The participants will be allocated using the method of simple randomization with an allocation ratio of 1:1, i.e. in two equal groups of 76 people, each.

The randomization of patients to the A ATM group and the B A-S group will be performed with the help of a random number generator created in Stata software with the help of the "randomizer" package. The "randomizer" package through the principles of binomial distribution, randomly assigns to each participant their participation in either the intervention group or the active control group. In this way each participant will be placed in one of two groups at the start of the study and will remain in the same group for the duration of the study. The ratio of subjects between the two groups will be maintained at 1:1 throughout the study.

This study is a single blind clinical trial. The intervention will be perceived by the principal researcher, who will apply the treatment protocol in the intervention group (A ATM), the physiotherapist, who will apply the treatment protocol in the active control group (B A-S) and the participants. It is not feasible for both participants and therapists to be blinded, due to the nature of each intervention. All evaluations of the effectiveness of the treatment interventions will be carried out by two independent assessors who, although belonging to the research team of the study, do not know the type of intervention that each patient will receive, as well as the allocation of patients to the different treatment intervention groups (Kang, 2013, Opara *et al.*,

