# 2.9. STATISTICAL ANALYSIS

Quantitative variables will be expressed as mean and standard deviation (SD). Qualitative variables will be expressed as absolute (N) and relative (%) frequencies. Pearson's  $\chi^2$  test and Fisher's exact test (where it is necessary) will be used to compare proportions, as well as McNemar test will be used to compare the percentages of kinesiophobia between measurements. Student's t-test or nonparametric criterion Mann-Whitney will be used for the comparison of the quantitative variables between the two groups. The change in the used scales and other indicators of the participants over time will be tested using linear mixed models from which dependence coefficients ( $\beta$ ) and their Standard Errors (SE) will be obtained. The group, the measurement (endline vs baseline) and their interaction term (to be tested in which extent the change is different between measurements in the two groups), will be introduced as independent variables. In the cases, where the interaction term will be found significant, sex, age, BMI and the symptoms duration will be introduced in the model (the chosen confounding factors are the most significant), in order to be tested if the interaction remain significant. Moreover, in the case that measurements at some outcome measures will be found to differ significantly at the initial measurement between the two groups, a result not due to systematic error but found to be due to random sampling. In these cases, their initial values will be entered into the mixed linear models as an independent variable to ensure that the findings from the models are not due to the initial differences between the groups. In cases that will be found significant differences between baseline measurements, between the two groups, the initial measurements will be introduced in linear mixed models as independent variable, in order to be ensured that the findings from these models are not due to initial differences between the groups. All reported p values will be two-tailed and statistical significance will be set at p < 0.05. Analyses will be conducted using the IBM SPSS Statistics 26.0.

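### The sample size rests on a two-group ANOVA, but 2.9 tests differential change by an interaction whose power depends on an unstated baseline-endline correlation, and no test is named for H0B1

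*Combined protocol and SAP*

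**What the plan says.** Section 2.5.1.1 bases the sample size on "the method of Analysis of Variance (ANOVA) in two groups of equal population, to identify a standardized effect size equal to 0.25", with 80% power and a 5% significance level. It defines the effect size as the absolute difference between the two group means of X divided by an SD, and adds that "SD is the Standard Deviation of X in the whole population". It reports that "the necessary sample size was calculated at 126 subjects" and then that "a dropout rate of 20% was expected, so a final number of around 152 patients is realistic for this study". It mentions no repeated measurement, change score or correlation between measurements.

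Section 2.9 analyses change over time with linear mixed models. The independent variables are "The group, the measurement (endline vs baseline) and their interaction term", and the interaction is there to test whether change differs between the two groups. The same section also lists a t-test or Mann-Whitney test for comparing quantitative variables between groups. It adds the baseline value to the mixed model only when the groups differ significantly at baseline, and states this rule twice.

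H0B1 in section 2.3 is the main between-group hypothesis: that ATM and A-S do not differ in their effect on pressure pain threshold (PPT). No sentence says which of the planned tests decides it.

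**The concern.** A two-group ANOVA on X and a group-by-measurement interaction have different precision. The ANOVA uses the SD of X. With two time points, the interaction is a comparison of changes, whose SD also depends on the baseline-endline correlation rho. The stated power carries over to the interaction only at one value of rho, and the documents give none.

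Two things are at stake. The reader cannot tell what power the trial has for its main between-group question. And the baseline, measured on everyone before treatment, is not used in the way that gives the most precise comparison and removes chance imbalance between arms.

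**Working it through.** **Inputs.** Power 80%, significance level 5%, effect size 0.25 and N = 126 (63 per arm) come from 2.5.1.1. Two-sided testing comes from 2.9: "All reported p values will be two-tailed and statistical significance will be set at p < 0.05". My assumptions, not in the documents: rho from 0 to 0.7, equal SDs at baseline and endline, and complete data on those analysed.

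**Reproducing 126.** The normal-approximation size per arm is 2(1.96 + 0.8416)²/d², where d is the mean difference over the SD.
- d = 0.5: 2 × 7.849/0.25 = 62.8, so 63 per arm and 126 in total. The noncentral F calculation gives 128; at 126 its power is 79.5%.
- d = 0.25: 2 × 7.849/0.0625 = 251.2, so 252 per arm and 504 in total.

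As a two-group comparison, 126 therefore fits only if 0.25 is Cohen's f, so that d = 2f = 0.5. The formula written in 2.5.1.1 makes 0.25 equal to d.

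**Power at N = 126 and d = 0.5.** The noncentrality parameter for one measurement is d√(63/2) = 0.5 × 5.612 = 2.806, giving 79.5% at any rho. For the interaction, the SD of change is SD√(2(1 − rho)), so the parameter is 2.806/√(2(1 − rho)). For the baseline-adjusted endline comparison the residual SD is SD√(1 − rho²), so it is 2.806/√(1 − rho²), ignoring the one degree of freedom spent on the covariate. The ratio of the adjusted variance to the interaction variance is (1 − rho²)/(2(1 − rho)) = (1 + rho)/2.

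| rho | Interaction: parameter | Interaction: power | Adjusted: parameter | Adjusted: power | Variance ratio |
|---|---|---|---|---|---|
| 0 | 1.98 | 50% | 2.81 | 79.5% | 50% |
| 0.3 | 2.37 | 65% | 2.94 | 83% | 65% |
| 0.5 | 2.81 | 79.5% | 3.24 | 90% | 75% |
| 0.7 | 3.62 | 95% | 3.93 | 97% | 85% |

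The N needed for 80% interaction power at d = 0.5 is 254, 178, 128 and 78 at these four values of rho.

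**With the expected dropout.** 152 × 0.8 = 121.6, about 122 completers. Interaction power is then 49%, 64%, 78% and 94%. Adjusted power is about 1 point or less below the column above.

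**With the effect size as defined (d = 0.25), N = 126.** Power is 29% for one measurement. At rho 0.3, 0.5 and 0.7 it is 22%, 29% and 44% for the interaction, and 31%, 36% and 50% for the baseline-adjusted comparison.

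**The conditional baseline rule.** In the mixed model of 2.9 the baseline is already one of the two responses. If it is also entered as a covariate with coefficient g, the term g × baseline appears in both of a patient's rows and cancels from the within-patient difference. With complete data the interaction estimate therefore stays equal to the raw difference in mean change. If the arms differ at baseline by an amount D by chance, and treatment makes no difference, the expected endline difference is rho × D (equal SDs). The change comparison is then off by −(1 − rho)D, with or without the covariate. Endline ANCOVA subtracts the estimated slope times D instead, which removes this.

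**The case against.** **The low figures are one side of an unknown.** A reader might infer that power for the main comparison falls to about 65%. The documents do not support that: 65% belongs to an assumed rho of 0.3. It is not a floor, since rho = 0 gives 50%, and above rho = 0.5 the interaction beats the stated 80%. Section 2.5.3.1.1 cites intra-rater ICCs for PPT of 0.84 to 0.93 and averages two readings, which does not point to a low rho. This stands. But those ICCs are not five-week correlations across a treatment period and two assessors, so they cannot supply rho in either direction.

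**Different assessors.** A reader might infer that using one assessor at baseline and another afterwards (2.5.1.2) must lower rho. It may, but it need not: one assessor takes all baselines and the other all endlines, so a constant offset between them leaves rho unchanged. For the craniocervical flexion test, 2.5.3.2.2 even cites a higher inter-rater ICC (0.86) than intra-rater ICC (0.63).

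**The ANOVA may match a planned test.** A reader might infer that the 80% belongs to a test the plan never uses. Section 2.9 also lists between-group t-tests, and 2.4(b) and 2.10 compare the groups after the intervention; the ANOVA would fit an endline comparison. Nor does the number settle which calculation was run. A within-between interaction with f = 0.125, two measurements and rho = 0.5 has noncentrality 126 × 0.125² × 2/(1 − 0.5) = 7.875 = 2.806², the same power, and needs 128. The wording of 2.5.1.1 describes no such calculation, but 126 alone cannot exclude it. What remains is that the deciding test is unnamed.

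**Validity.** Under randomisation the interaction is a valid, unbiased test, so preferring baseline adjustment is a choice about efficiency and chance imbalance. That is right, and it limits the point to power and precision.

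**Conclusion.** The point holds in a limited form. The plan does not say which test decides H0B1, and the power of the interaction in 2.9 cannot be read from 2.5.1.1 because rho is missing. At d = 0.5 and equal SDs it is below the stated 80% if rho is under 0.5 and above it if rho is higher. The documents do not show which case applies, so this is not a finding that the trial is underpowered for that reason.

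Two conclusions do not depend on rho. The baseline-adjusted comparison has at least the power of the two-group ANOVA and at least that of the interaction across the range examined. And the conditional covariate rule does not do what 2.9 intends, because it leaves the interaction estimate unchanged when data are complete.

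Every d = 0.5 figure rests on reading 0.25 as Cohen's f. The contradiction with the definition in 2.5.1.1 is the larger problem for power, and stating rho will not repair it.

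**What to change.** In 2.9:
- Name the baseline-adjusted endline difference between arms as the test of H0B1.
- Use the same estimate for every outcome measured at baseline, either by ANCOVA on the endline value or by a mixed model with baseline means constrained equal across arms (no group main effect). The Global Perceived Effect (2.5.3.2.11) is exempt, since it is a single retrospective rating without a baseline value.
- Delete both statements of the conditional baseline-covariate rule. Otherwise the baseline could enter the constrained model as both response and covariate.

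In 2.5.1.1:
- Say whether 0.25 is Cohen's f or the mean difference over the SD, and make the formula and N agree.
- Restate power for the named test with an assumed rho, its source and a range. If d = 0.5 is intended, the adjusted-power column above gives the figures for 126 analysed; those for about 122 completers should stand beside them.

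The cost is a few sentences in two sections, with no extra patients, visits or data.

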2013). The first assessor will administer the consent form, the demographic characteristics form, the questionnaires and recorded the primary outcome measures, as well as the secondary outcome measure prior to the start of the study. The second assessor will administer the compliance and complaint form to the participants and will record the primary outcome measure and the secondary outcome measures after the completion of the interventions. Data analysis will be performed by an independent biostatistician, an associate of the Musculoskeletal Physiotherapy Research Laboratory of the University of West Attica (UNIWA), who will not know the group in which each participant will have been allocated.

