#### 2.5.3.1. PRIMARY OUTCOME MEASURE

#### 2.5.3.1.1. PAIN SENSITIVITY (PRESSURE ALGOMETER)

The primary outcome measure will be the pain sensitivity and a pressure algometer (Commander® Algometer, JTECH Medical, Midvale, Utah) will be used, measuring the Mechanical Pain Threshold (MPT). This model is a handheld algometer with two different heads (with surface of 0.5 cm^2, 1 cm^2), a flat pad and a fingertip adapter. The maximum input force reaches 111 N, while the wireless radio frequency (RF) reaches 2.4 GHz. The head which will be used has an area of one square centimeter (1cm^2) and the unit of measurement for the MPT value is kilogram per square centimeter (kg/cm^2).

In this PhD thesis, the recording of the pain sensitivity will be performed at specific points such as the upper part of the trapezius muscle and the suboccipital region, as the pressure algometer has shown high intra-rater reliability when applied to the upper trapezius muscle (Intraclass Correlation Coefficient / ICC: 0.85-0.86) and the suboccipital region (ICC: 0.84-0.93) in patients with chronic non-specific neck pain (Pérez-Martínez *et al.*, 2020). The measurement in the suboccipital region will be performed at the mastoid process and at the BL 10 point, which is located on the horizontal line that passes between the spinous processes of the C1 and C2 vertebrae and the oblique line that passes through the outer border of the upper part of the trapezius muscle. It is exactly 1 cm on either side of the vertical axis of the body, which passes through the spinous processes of the C1 and C2 vertebrae. In the upper trapezius muscle, the measurement point is between the midline and the lateral border of the acromion (Wang-Price *et al.*, 2019). In addition, measurements will be made at the zygopophyseal joint between C5-C6 intervertebral space (1/2

Cun), at the tibialis anterior muscle (Stomach 36/ST 36), at the middle part of the deltoid muscle (1-2 cm below the acromion) as well as in the levator scapula muscle (2 cm above its epiphysis, at the upper medial angle of the scapula) (Wang-Price *et al.*, 2019).

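### Section 2.5.1.1: the stated effect size (0.25), its printed definition, 80% power and 126 subjects cannot all be true; 126 corresponds to about 0.50 SD

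*Combined protocol and SAP*

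**What the plan says.** Section 2.5.1.1 describes an ANOVA with two equal groups, intended "to identify a standardized effect size equal to 0.25 with a power of 80% and a level of statistical significance of 5" per cent. It prints the formula for the effect size as |μA − μB|/SD and adds that "SD is the Standard Deviation of X in the whole population". The calculation is credited to G*Power, and "the necessary sample size was calculated at 126 subjects". The section then says "a dropout rate of 20% was expected, so a final number of around 152 patients is realistic for this study", and section 2.5.1.2 allocates these "in two equal groups of 76 people, each".

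Section 2.9 makes all tests two-tailed at 5%. It tests change over time with a linear mixed model whose terms are given as "The group, the measurement (endline vs baseline) and their interaction term". Nowhere does the plan give an SD in kg/cm², a clinically important difference or a correlation between baseline and five-week values, and it does not mention Cohen's f.

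**The concern.** The formula in section 2.5.1.1 is that of a standardized mean difference. A difference of a quarter of an SD between two groups is small, and 63 per group is far too few to detect it with 80% power in a two-group comparison. Either the effect size is mislabelled or the power is misstated.

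This is the plan's only statement of what the trial can detect. The comparator is active, and section 2.10 lists a non-significant difference between groups as one of the results to be reported. A reader who takes the paragraph at face value could read a null result on the main between-group hypothesis (H0B1, pressure pain threshold) as evidence against differences of 0.25 SD, when the number of subjects suits a difference about twice that size.

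**Working it through.** **Inputs.** Effect size 0.25, defined as d = |μA − μB|/SD; two equal groups; 80% power; 5% level; 126 subjects, so 63 per arm (all section 2.5.1.1). Two-sided testing (section 2.9). Enrolment 152, or 76 per arm (section 2.5.1.2). Expected dropout 20% (section 2.5.1.1).

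**Reproducing 126.** The normal approximation is n per arm = 2(1.960 + 0.842)²/d².

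- d = 0.50: 2 × 7.849/0.25 = 62.8, so 63 per arm, **126** in total. This is the plan's figure.
- d = 0.25: 2 × 7.849/0.0625 = 251.2, so 252 per arm, 504 in total.

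**Exact calculation.** A two-group ANOVA is equivalent to a two-sided t-test. Power comes from the noncentral t with 2n − 2 degrees of freedom and noncentrality d√(n/2). At 63 per arm the noncentrality is 0.25 × √31.5 = 1.403 for d = 0.25 and 2.806 for d = 0.50.

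| Subjects analysed | Power, 0.25 SD | Power, 0.50 SD | Detectable at 80% power |
|---|---|---|---|
| 122 (61 per arm) | 27.8% | 78.2% | 0.51 SD |
| 126 (63 per arm) | 28.6% | 79.5% | 0.50 SD |
| 152 (76 per arm) | 33.4% | 86.5% | 0.46 SD |

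The exact N for 80% power is 506 (253 per arm) at 0.25 SD and 128 (64 per arm) at 0.50 SD.

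**Other readings of the paragraph.**

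- *One-sided test:* 0.25 SD needs 396 (normal) or 398 (exact).
- *SD as the total SD, including the spread between groups:* the within-group difference is 0.25/√(1 − 0.25²/4) = 0.252. Power at 126 is 28.9%, and 498 are needed.
- *0.25 as Cohen's f:* with two equal groups f = d/2, so f = 0.25 means d = 0.50, which gives 126 (normal) or 128 (exact).

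Only the last reading comes near the plan's figure.

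**The mixed-model interaction of section 2.9.** With complete data and equal variances at both visits, the group-by-measurement term is a comparison of change scores, with effect 0.25/√(2(1 − r)), where r is the pre-post correlation. If the baseline value is entered as a covariate, the effect is 0.25/√(1 − r²). Because r is not given, it is an assumption and is shown as a range, with 63 per arm:

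| r (assumed) | Change score | Baseline-adjusted |
|---|---|---|
| 0.5 | 29% | 36% |
| 0.8 | 60% | 64% |
| r needed for 80% power | about 0.88 | about 0.87 |

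**Dropout.** 126 × 1.2 = 151.2, which is where 152 comes from. To keep 126 after losing 20%, 126/0.8 = 157.5, so 158 are needed. Conversely, 152 × 0.8 = 121.6, about 122 completers, and 152 protects 126 only up to a loss of 1 − 126/152 = 17%. At 0.50 SD the shortfall costs 79.5 − 78.2 = 1.3 points of power.

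**The case against.** The strongest defence is that f = 0.25 was evidently used, so the number of subjects is about right and only a formula is misprinted. That is plausible, but the plan never names f, and exact two-group ANOVA with f = 0.25 gives 128 rather than 126; the match to 126 needs the normal approximation. The cause therefore remains an inference. If it is correct, the printed definition understates the target difference by a factor of two, which is the defect at issue.

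A second defence is that section 2.9 tests an interaction, which gains from repeated measurement. This stands in part: 28.6% is the power of the comparison that section 2.5.1.1 describes, not of every analysis in the plan. But 80% power for 0.25 SD would need a correlation of about 0.88 that is nowhere stated. The algometer reliabilities in section 2.5.3.1.1, such as "the suboccipital region (ICC: 0.84-0.93) in patients with chronic non-specific neck pain", do not supply it. They are intra-rater figures, not five-week correlations, and under section 2.5.1.2 one assessor takes the baseline values while a second "will record the primary outcome measure and the secondary outcome measures after the completion of the interventions".

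Two further points are fair. The dropout shortfall is minor, and the plan says only that the total is around 152. And if 0.25 SD with 80% power was truly the aim, enlarging the trial would also be coherent; that is the sponsor's decision and is not needed to correct the text.

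**Conclusion.** The contradiction holds and must be fixed. Under the printed definition, 126 subjects have about 29% power for 0.25 SD in a two-sided two-group comparison, against the 80% stated, and 80% would take 506, about four times as many. The figure of 126 matches about 0.50 SD. The discrepancy is far too large to be rounding, and neither one-sided testing nor the total-SD reading removes it. The result rests on equal groups, a two-sided 5% level and a common SD. Power for the mixed-model interaction cannot be stated without a pre-post correlation. The dropout error is real but secondary.

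**What to change.** In section 2.5.1.1, state which effect size was meant and make the rest agree with it:

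- If 0.50 SD was meant, give the effect as f = 0.25, equivalent to |μA − μB|/SD = 0.50, and note that the exact N is 128.
- If 0.25 SD was meant, keep the definition and correct the stated power.

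In either case, report what 152 enrolled with 20% loss (about 122 completers) delivers in the two-group comparison: about 78% power for 0.50 SD, about 28% for 0.25 SD, and a detectable difference of about 0.51 SD at 80% power. Alternatively for the dropout sentence, say that 152 keeps 126 up to a 17% loss. If the sponsor wishes to rely on the mixed-model interaction, state the assumed pre-post correlation and the power it gives.

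The cost is one rewritten paragraph. No extra patients are needed, and randomization and analysis do not change. Either the stated detectable difference or the stated power will look less favourable than it does now.

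### The 20% dropout allowance is added to 126 instead of being taken from those enrolled, so 152 patients leave about 122, not the necessary 126 (a minor error)

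*Combined protocol and SAP*

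**What the plan says.** Section 2.5.1.1 (Sample characteristics) of the combined protocol and SAP gives the sample size in three steps. First, "the necessary sample size was calculated at 126 subjects". Second, 20% dropout is forecast. Third, the enrolment figure is presented as following from these two: "a dropout rate of 20% was expected, so a final number of around 152 patients is realistic for this study". No inflation formula is shown and no other reason for 152 is offered.

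Section 2.5.1.2 (Method of randomization and blinding) then fixes the figure: "The sample will include 152 patients of both sexes and age range 19-70 years", with an "allocation ratio of 1:1, i.e. in two equal groups of 76 people, each".

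Section 2.8 (Procedure) says that the cumulative dropout rate will be worked out from the total sample. Section 2.9 (Statistical analysis) plans linear mixed models with group, measurement (endline against baseline) and their interaction, tested two-sided: "All reported p values will be two-tailed and statistical significance will be set at p < 0.05".

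**The concern.** An allowance for dropout should be large enough that, if the forecast loss occurs, the required number of patients is still left. Losses come out of the patients enrolled, so the required number has to be divided by the retained share. Adding the dropout percentage to the required number always gives a smaller total, and the gap widens as the rate rises.

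Here the word joining the forecast to 152 tells the reader that 152 is enough to keep 126 at 20% dropout. If it is not, an ethics committee or a later reader will take the necessary number as secured when, on the plan's own forecast, the trial is expected to finish below it.

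**Working it through.** **Inputs**

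- Necessary number: 126 in total (section 2.5.1.1).
- Expected dropout: 20% (section 2.5.1.1).
- Planned enrolment: 152, or 76 per arm (section 2.5.1.2).
- Two-sided 5% level (sections 2.5.1.1 and 2.9).

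**Step 1. Reproduce the plan's figure.** Required number × (1 + dropout) = 126 × 1.20 = 151.2, rounded up to 152. This matches exactly, so the 20% was applied to 126.

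**Step 2. Patients left under the plan's own forecast.** Enrolled × (1 − dropout) = 152 × 0.80 = 121.6, about 122, or about 61 per arm. The shortfall is 126 − 121.6 = 4.4 patients (4.4 / 126 = 3.5%).

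**Step 3. Enrolment that would keep 126.** Required number / (1 − dropout) = 126 / 0.80 = 157.5, so 158 (79 per arm). Check: 158 × 0.80 = 126.4. The difference from the plan is 158 − 152 = 6 patients.

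**Step 4. Dropout that 152 can absorb.** 152 − 126 = 26 losses, and 26 / 152 = 17.1%. A 27th loss leaves 125.

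**Step 5. Cost in power.** This step needs an effect size. The plan states 0.25 and defines it as the difference in means divided by the SD, but that value does not give 126. The normal-approximation formula gives 126 for a difference of 0.50 SD (63 per arm, two-sided 5%, 80% power). I therefore show both, using the two-sample t-test:

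| Assumed difference | Power at 126 | Power at 122 | Loss |
|---|---|---|---|
| 0.50 SD (reproduces 126) | 79.5% | 78.2% | 1.3 points |
| 0.25 SD (definition in 2.5.1.1) | 28.6% | 27.8% | 0.8 points |

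At the unrounded 121.6 the first row gives 78.1%, a loss of 1.4 points. On either assumption, the dropout arithmetic changes power by less than 1.5 points.

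**Step 6. Chance of keeping 126.** If each patient independently has a 20% chance of dropping out, the probability that at least 126 remain is about 22% with 152 enrolled and about 58% with 158 enrolled.

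**The case against.** **The figures are approximate.** The text says around 152, and 20% is only a forecast. By the t-test even 126 falls slightly short of 80% power at 0.50 SD (127.5, so 128, would be needed), so 126 is not a sharp limit. All of this is true, and it is why the point is minor. It does not repair the statement: 152 is exactly 151.2 rounded up, and section 2.5.1.2 fixes it as the enrolment.

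**Perhaps 20% was meant as a share of 126.** The documents point the other way. Section 2.8 takes the dropout rate from the total sample, although that sentence concerns the patients who attend follow-up. On that base a 20% rate means about 122 remaining.

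**Perhaps mixed models make completers less important.** With the two measurements in the model, a patient lost before endline supplies a baseline value and no observed change. The group-by-measurement interaction therefore rests mainly on those who complete.

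**Stronger readings that a reader might infer, and that the documents do not support:**

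- *That the trial has no protection against withdrawal.* It has protection up to 17.1%, about 3 percentage points short of what is claimed.
- *That dropout monitoring would miss the problem.* No section describes a retention limit or a trigger for action on dropout, so there is nothing for the error to mislead.
- *That a 22% chance of keeping 126 shows a serious failure.* Correct inflation to 158 would give only about 58%, because inflating for expected dropout never guarantees the target.
- *That section 2.5.1.2 is a second error.* It only repeats the enrolment target.

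**Conclusion.** Wrong as written, minor in severity. On the plan's own inputs, 152 enrolled and 20% dropout leave about 122 patients, about 4 fewer than the number called necessary. The 126 is kept only if no more than 26 patients are lost.

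This result takes 126 as the plan's stated requirement and 20% as a share of those enrolled. It does not depend on how 126 was derived. The power figures do: the fall from 79.5% to about 78% assumes a 0.50 SD difference, which the plan does not state.

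A reader might conclude that the dropout arithmetic leaves the trial underpowered. It does not, because its effect is little more than one point. The statement "to identify a standardized effect size equal to 0.25" and the definition attached to it do conflict with 126, on a much larger scale, but that is a separate issue and should be dealt with on its own.

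**What to change.** Keep enrolment at 152 and replace the dropout sentence in section 2.5.1.1 with wording such as:

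> *152 enrolled patients leave about 122 at the expected 20% dropout; the necessary 126 is retained only if dropout is at most about 17% (26 patients).*

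If a power for about 122 patients is added, it must name the effect size it assumes. It is best added after the meaning of 0.25 has been settled; printing about 78% beside 0.25 as now defined would create a new contradiction.

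Section 2.5.1.2 needs no change, and no monitoring limit needs to be added. The cost is one sentence: no extra patients and no change to procedures or analysis. The stated position becomes slightly less favourable.
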